August 20th 2021

ClinicalTrial.gov

Transcranial Direct Current Stimulation Therapy for Central Hypersomnia Without Cataplexy

NCT Number: NCT03198156

[name]

The Ohio State University

Professor of Medicine and Neuroscience

Division of Pulmonary, Critical Care, and Sleep Medicine

Director Sleep Disorders Center

[name]

[name]

Office: [name]/Clinic: [contact]

**Title: Transcranial Direct Current Stimulation Therapy for Central Hypersomnia
Without Cataplexy**

Principal Investigator:

[name] M.D.
Professor of Medicine and Neuroscience
Director, Sleep Medicine Program
[name]
[name]
[name]
[contact]
[contact]

Co-investigators:

[name]
Assistant Professor of Medicine and Neurology
Department of Neurology
[name]
[name]
[contact]
[contact]
Email: [contact]

[name]
Research Scientist
Center for Biostatistics
The Ohio State University
College of Medicine Department of Biomedical Informatics
[name]
[contact] Office
[contact]

External Collaborators:

R. [name]
Applied Neuroscience Branch, [name], USA
Air Force Research Laboratory
711 HPW/RHCP
[name]
[name]
[name]
[contact]
E-mail: [contact]

Performance Sites:

The Ohio State University Wexner Medical Center

IND number:

Not applicable

IDE: non-significant risk (NSR) investigational device that meets the abbreviated Investigational Device Exemptions (IDE) requirements at 21 CFR 812.2(b)

Funding: Center for Brain Health and Performance

Table of Contents

I.	Objectives
II.	Background and Rationale
III.	Procedures.....
	A. Research Design.....
	B. Subject selection.....
	1. Inclusion/Exclusion criteria.....
	2. Vulnerable populations.....
	3. Populations vulnerable to undue influence or coercion.....
	4. Inclusion of women and minorities.....
	C. Study Plan
	Study Schema.....
	D. Detailed procedures.....
IV.	Data Analysis.....
V.	Event Reporting
VI.	Ethical Considerations
VII.	Data Handling and Record Keeping.....
VIII.	Data and Safety Monitoring Plan.....
IX.	References.....

I. Objectives

- 1) To determine the effects of transcranial direct current stimulation (tDCS) on vigilance in subjects with central hypersomnia without cataplexy.

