- Idiopathic Hypersomnia or Narcolepsy without Cataplexy (Narcolepsy Type 2). Idiopathic hypersomnia and narcolepsy without cataplexy are usually objectively differentiated based on the number of sleep onset rapid eye movement periods (SOREMP) during a multiple sleep latency test (MSLT). However, this diagnostic feature has been shown to be not stable over time making it difficult for clinicians to distinguish these two conditions.^{16,17}
- Hypersomnia in OSA patients adequately treated with positive airway pressure (PAP) therapy or dental device
- Posttraumatic hypersomnia
- Unspecified hypersomnia

Patients with Narcolepsy with Cataplexy will be excluded from this study in view of the specific known loss of hypocretin in these patients.

Informed consent will be obtained from all participants. If the subject is agreeable, the consent form will be sent to them via mail or electronically so that they will have the opportunity to read the document ahead of time.

B. Subject Selection:

1. Inclusion/Exclusion Criteria

A. Key Inclusion Criteria

- Age 18 - 70 years
- Epworth Sleepiness scale score >10
- Stable medication dosage over previous 4 weeks
- Able to understand English and read and write at the 8th grade level and give a written informed consent document.
- Stable sleep/wake schedule (that is, no rotating shift work)
- Clinical diagnosis of any of the following:
 - a. Idiopathic Hypersomnia
 - b. Narcolepsy without Cataplexy
 - c. Hypersomnia in OSA patients adequately treated with PAP therapy or dental device

- d. Posttraumatic hypersomnia
- e. Hypersomnia, unspecified
- Multiple sleep latency test (MSLT) shows fewer than two sleep onset REM periods (except for patients with Narcolepsy without cataplexy, a diagnosis that requires at least two sleep onset REM periods) and a mean sleep latency of \leq 8 minutes. An MSLT is not required for inclusion of OSA patients provided their Epworth Sleepiness Scale (ESS) score is >10 . Adequately treated OSA patients will be defined as: i) an average PAP usage of \geq 4 hours per night and a residual apnea-hypopnea index (AHI) of <10 /hour based on PAP machine download during at least a 30-day period, or ii) regular use of dental device during sleep based on self-report and a prior sleep study showing an AHI <10 /hour while using the dental device.

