- Subjects with idiopathic hypersomnia with an MSLT mean sleep latency of > 8 minutes will be included provided they have hypersomnia symptoms and habitually long sleep times (average of ≥ 10 hours per day) documented by actigraphy for at least 7 days.¹⁸
- Subjects currently on stimulant medications who upon discussion with their sleep medicine provider, are either scheduled to be on a medication holiday or are willing to discontinue their stimulants for at least one week before study enrolment, will be eligible for the study. Eligibility will be determined via a clinician note in the medical record stating the above plan.

B. Key Exclusion Criteria

- Self-reported habitual sleep period of < 7 hours/night
- History of automobile accident due to falling asleep while driving within the past 2 years
- Currently taking stimulant medications such as Modafinil, Armodafinil, Methylphenidate, or Dextroamphetamine.
- Inability to understand or read English
- Clear history of cataplexy
- Moderate or severe sleep apnea defined as an apnea-hypopnea index (AHI) of ≥ 15 /hour based on a previous sleep study and non-compliant with treatment.
- Self-reported Substance abuse (current)
- Excessive alcohol consumption defined as:
 - More than 3 glasses of wine a day
 - More than 3 beers a day
 - More than 60 mL of hard liquor a day
- Presence of cardiac pacemaker or automatic implantable cardioverter-defibrillator (AICD).
- Pregnancy, lactation (will be screened with urine pregnancy test)
- Recent hospitalization for major surgery/major illness (within past 1 month)
- Non-removable metal or tattoos around head
- Use of implantable birth control device such as Implanon
- History of severe and frequent headaches
- Unstable coronary artery disease
- Uncontrolled Seizure disorder

- Uncontrolled hypertension
- Uncontrolled Congestive heart failure
- Anything that, in the opinion of the investigators, would place the subject at increased risk or preclude a participant's full compliance in completing the study

2. Vulnerable Populations

- Children, fetuses, neonates, or prisoners are not included in this research study.

3. Populations vulnerable to undue influence or coercion

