Should an OSU employee or student (or their surrogate) be approached for enrollment, they will be given the opportunity and time to consider participation and will be reassured that declining to participate will not jeopardize or hinder their standard of care at the OSU Wexner Medical Center, nor will it have any bearing on either their student status or employment.

4. Inclusion of Women and Minorities

Both men and women of all races and ethnic groups are eligible for this study.

C. Study Plan

This is a randomized, sham-controlled, parallel group study. The study will last up to 5 weeks. After informed consent, subjects with idiopathic hypersomnia with an MSLT mean sleep latency of >8 minutes will undergo actigraphy and those with an average sleep time of ≥ 10 hours per day will continue with the study while those with <10 hours sleep time will be excluded. In addition, OSA subjects with complaints of hypersomnia with an ESS score <10 will also be excluded. Female subjects of child bearing age and not menopausal will have a pregnancy test performed as pregnancy is an exclusionary criteria.

Subjects will be randomized to receive either active tDCS or sham stimulation for 30 minutes daily for 4 sessions. The randomization scheme will be generated in permuted blocks of varying size. The randomization scheme will be prepared, uploaded, and overseen by the study's biostatistician. Investigators and research staff, other than the biostatistician, will not have access to the full randomization scheme. Randomization assignments will be delivered via RedCap.

Subjects will be blinded as to whether they are receiving sham or active tDCS treatments. The investigator who will conduct the analysis of all outcomes will be blinded as to subject treatment assignment.

All stimulation visits will be completed within a five-consecutive day period; that is one stimulation visit may be missed provided a total of four stimulation visits are completed within a five-day period. Outcome measures will include: psychomotor vigilance test (PVT), subjective measures of sleepiness, and the Center for Epidemiologic Studies Depression (CES-D) scale. PVT will be performed pre- and post- stimulation during the first and last stimulation sessions. Subjective measures of sleepiness include the following: Epworth Sleepiness Scale (ESS), Stanford Sleepiness Scale (SSS), Functional Outcomes of Sleep Questionnaire-10 (FOSQ-10), and Visual Analogue Scale (VAS).

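### Treated OSA is the only diagnosis admitted without objective evidence of sleepiness, yet OSA status is not a randomisation stratum, a covariate or a planned supportive analysis

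*Combined protocol and SAP*

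**What the plan says.** **Target population.** Section I states the first objective as the effect of tDCS "on vigilance in subjects with central hypersomnia without cataplexy". Section II counts hypersomnia due to medical disorders among the central disorders of hypersomnolence. Section III.A and the inclusion list in III.B.1 name hypersomnia in adequately treated OSA as an eligible diagnosis.

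**Evidence of sleepiness.** Section III.B.1 requires "Epworth Sleepiness scale score >10" of everyone. The other diagnoses also need an MSLT mean latency of 8 minutes or less. Idiopathic hypersomnia with a longer latency needs at least 10 hours of sleep a day on actigraphy instead. For OSA: "An MSLT is not required for inclusion of OSA patients provided their Epworth Sleepiness Scale (ESS) score is" above 10.

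**Adequate treatment of OSA (III.B.1).** On PAP, the requirement is average use of at least "4 hours per night and a residual apnea-hypopnea index (AHI) of <10 /hour based on PAP machine download during at least a 30-day period". The alternative is "regular use of dental device during sleep based on self-report and a prior sleep study showing an AHI" below 10/h on the device, with no threshold for hours of use. The exclusion criteria remove anyone with "Self-reported habitual sleep period of < 7 hours/night".

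**Allocation and analysis.** Section III.C says: "The randomization scheme will be generated in permuted blocks of varying size". It names no stratification factor. In Section IV each co-primary regression adjusts only for the baseline value of its own endpoint. No diagnosis term, subgroup or sensitivity analysis by diagnosis is specified, and no cap on the number of OSA patients is stated.

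**The concern.** The condition attached to the MSLT waiver adds nothing, because the same ESS score is a general entry criterion. OSA patients therefore enter with self-reported sleepiness, a clinical diagnosis and a treatment definition, while every other patient also has an objective measurement.

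That leaves the treatment definition to separate residual central sleepiness from sleepiness caused by apnoea that is still partly untreated. It does so imperfectly. The download AHI covers only the hours with the device on, and the dental route relies on self-report for use. Some OSA entrants may thus be incompletely treated.

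What is at stake is interpretation first and chance balance second. If the overall result is positive or null, a reader will ask whether it also holds in patients whose hypersomnia was objectively documented. The plan has no pre-specified answer, although OSA status is known for every patient at entry.

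**Working it through.** **1. The plan's own figure.** Inputs from Section IV: 60 randomised, at least 50 evaluable (25 per arm), two-sided alpha 0.025, and effects of 0.90 SD in mean 1/RT and 2.87 ESS points with SD 3.2. A two-sample t-test (noncentral t) gives 80.4% power for 0.90 SD and 80.1% for 2.87/3.2 = 0.897 SD. The stated 80% reproduces.

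**2. Hours the PAP rule can leave uncovered.** The minimum habitual sleep period is 7 h and the minimum average PAP use is 4 h. A patient at both limits has 7 − 4 = 3 h off PAP, or 3/7 = 43% of the period. This equates a self-reported sleep period with hours asleep, and it describes the boundary of the rule, not a typical patient.

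**3. Chance imbalance in OSA share.** The documents give no OSA share, so I assume p = 20% to 50%. With 25 per arm, the SD of the between-arm difference is √(2p(1 − p)/25). With 60 patients split 30:30 at a fixed OSA total, the chance of a difference of at least 20 points (6 or more patients) comes from the hypergeometric distribution.

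| Assumed share p | SD of difference, 25 per arm | Chance of ≥20 points, 30 per arm |
|---|---|---|
| 20% | √(0.32/25) = 11.3 points | 10% |
| 30% | √(0.42/25) = 13.0 points | 16% |
| 40% | √(0.48/25) = 13.9 points | 19% |
| 50% | √(0.50/25) = 14.1 points | 20% |

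**4. What an imbalance could do to the estimate.** Let d be the OSA versus non-OSA difference in the Visit 4 outcome, in SD units, that remains after baseline adjustment. The shift in the treatment estimate is about d × imbalance. The documents do not give d. For a 20-point imbalance:
- d = 0.25: 0.25 × 0.20 = 0.05 SD
- d = 0.50: 0.50 × 0.20 = 0.10 SD
- d = 1.00: 1.00 × 0.20 = 0.20 SD

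The standard error of the unadjusted difference is √(2/25) = 0.28 SD, so even the largest of these shifts is smaller than one standard error.

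**5. Precision of the supportive estimates.** The approximate 95% half-width before baseline adjustment is 1.96 × √(2/n per arm), times 3.2 for ESS points.
- All patients, 25 per arm: 0.55 SD (1.8 points).
- Share 20%: non-OSA, 20 per arm, 0.62 SD (2.0 points); OSA, 5 per arm, 1.24 SD (4.0 points).
- Share 50%: each group, 12.5 per arm, 0.78 SD (2.5 points).

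**The case against.** The strongest reply is that OSA patients belong to the population the sponsor declared. Sections II and III.A place treated OSA with residual hypersomnia within it, randomisation protects the comparison, and baseline adjustment absorbs much of any difference in PVT or ESS level. All of that stands. The objection that other diagnoses are mixed too is also fair, but OSA is the only one admitted on a different standard of evidence, which is why it is the natural stratum. Section IV does allow exploratory analyses and summarises characteristics by arm, but neither is a pre-specified result by OSA status.

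Four stronger readings are tempting and are not supported:

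- **That OSA patients enter on ESS alone.** They also need a clinical diagnosis and must meet the treatment definition. Only the objective evidence of sleepiness is missing.
- **That the overall result cannot be attributed to central hypersomnia.** This substitutes a narrower definition for the protocol's own. What survives is possible misclassification of under-treated patients.
- **That an eligible patient's whole-night AHI breaches the protocol's 15/h line.** That line refers to a previous sleep study and excludes only patients who are also non-compliant with treatment. A time-weighted index would need off-PAP sleep hours and untreated AHI, neither of which the documents supply, so any value is hypothetical.
- **That power is lost.** If OSA patients had half the 0.90 SD effect and made up 20% of the sample, power would be 71%. But nothing in the documents indicates a different response in OSA.

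**Conclusion.** The concern holds as a modest gap in design and analysis, not as a flaw in the treatment comparison. One diagnosis enters on weaker evidence, its treatment definition may admit some incompletely treated patients, and the plan neither balances nor adjusts for that diagnosis, nor reports by it.

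The number of affected patients is unknown. For assumed OSA shares of 20% to 50%, the arms would differ in OSA share with an SD of 11 to 14 points. The effect of such an imbalance on the estimate is likely to be small relative to its standard error unless OSA status predicts outcome strongly beyond baseline. The main gain is therefore interpretive: a pre-specified view of the result in patients with objectively documented hypersomnia. The change is worth making because it is cheap.

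**What to change.** 1. Stratify the REDCap permuted blocks by OSA versus all other diagnoses. If randomisation has begun, leave the scheme alone and fix OSA status as a covariate only, before any unblinding.
2. Add OSA status to both co-primary regressions alongside the baseline value. Use the same models at the interim analysis (34 completers) and the final analysis.
3. Pre-specify the treatment estimate with its confidence interval in non-OSA and in OSA patients, for both co-primary endpoints. Label these supportive, outside the alpha allocation.

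No change to the eligibility or PAP rules is proposed. A sensitivity analysis on whole-night AHI is not recommended: the plan does not list the data it needs as collected, and it could not cover dental-device users.

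Cost: slightly more incomplete blocks, one degree of freedom per model and one extra table. OSA status is already established at eligibility. The subgroup intervals will be wide, as step 5 of the working shows, and should be read as consistency checks rather than tests.

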We will use a custom set of silver/silver chloride electroencephalographic (EEG) electrodes as described in McKinley et al.²¹ These new electrodes were shown to be more stable over time, produce lower sensation levels, and produce fewer skin reactions when compared to standard sponge electrodes. Both the anode and cathode consist of a separate array of 5 EEG electrodes as pictured in Fig. 1. Each electrode has an inner diameter of 1.6 cm yielding a contact area of 2.01 cm² for each electrode. At 2 mA of supplied current, the average current density will be 0.199 mA/cm² as calculated by current (2 mA) divided by area (10.05 cm²).

For the active anodal stimulation condition, tDCS will be applied at 2mA for 30 min. Sham tDCS will be applied at the same intensity but for only 30 seconds.¹ The anode will be applied to scalp location F3 according to the 10-20 EEG electrode placement system while the cathode will be placed over the contralateral (i.e. right) bicep. Electrodes will be secured using medical bandages, and connectivity will be ensured using highly conductive gel.¹

IV. Data Analysis

Sample size:

The sample size is selected such that we have power to detect differences in the mean reciprocal reaction time (mean 1/RT) and ESS, which are our co-primary endpoints. Differences in co-primary endpoints will be assessed at Visit 4. We assume a loss to follow up rate of 15%.

We will enroll a total of 60 patients with 30 randomized to each group. Thus we anticipate at least 50 evaluable patients. We will control the type I error rate at 0.05 for assessing the primary endpoints conservatively using a Bonferroni correction. With this sample size, we have 80% power to detect a change of 0.90 standard deviations in mean 1/RT with an alpha level of 0.025 using a two-sided t-test. For the ESS, we assume a standard deviation of 3.2²² and have 80% power with this sample size to detect a change in ESS of 2.87 with an alpha level of 0.025 using a two sided t-test.

Statistical Methods:

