The primary analysis will examine the co-primary endpoints. To analyze differences in mean 1/RT at Visit 4, we will use a linear regression model that is adjusted for baseline average inverse response time. To analyze differences in ESS at Visit 4, we will use a linear regression model that is adjusted for baseline ESS. We will employ a sequential testing procedure to control familywise type I error at 0.05 where we first test differences mean 1/RT and then test ESS.²³ If an endpoint is not stopped for early efficacy, it will be tested at the remaining alpha level, 0.023. If there is a significant difference in mean 1/RT, then ESS will instead be tested at the total remaining alpha level, 0.046.

Figure 1. tDCS electrode array (anode only pictured). All five elements are standard silver-silver chloride EEG electrodes placed in a plastic cup which is then filled with a conductive gel.¹

Secondary analyses will include additional outcomes from the PVT and subjective questionnaires. To analyze differences in the number of lapses at Visit 4, we will use a Poisson regression model to compare the lapse rate of the treatment group to that of the control group that adjusts for the baseline lapse rate. Additional subjective sleep scores and questionnaires will be assessed using linear regression that adjusts for baseline sleep and questionnaire scores respectively. We will also explore differences in the magnitude of the change pre and post treatment at Visit 1 and pre and post treatment at Visit 4. Characteristics of participants will be summarized by randomized treatment group using appropriate descriptive statistics. We will also summarize any reported side effects of treatment. Additional exploratory analyses may be conducted at the discretion of the study team.

Interim Analysis

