An interim analysis will be conducted after 34 patients have completed the study. The study will be stopped early for efficacy if both endpoints achieve the stopping boundaries. The analysis will assess both co-primary endpoints using the error spending approach described by Lan and Demets with the O'Brien-Fleming boundary.^{24,25} For reaction time, the stopping boundary will be achieved if the two-sided p-value is less than 0.005 ($|Z|>2.813$). If early efficacy is achieved for reaction time, early efficacy for ESS will be evaluated and calculated using the total available type I error rate of 0.05. In that case, the stopping boundary will be achieved if the one-sided p-value is less than 0.013 ($|Z|>2.48$). If early efficacy is not achieved for reaction time, then the stopping boundary for ESS will be achieved if the two-sided p-value is less than 0.005 ($|Z|>2.813$).

V. Event Reporting

(a) Adverse Events

The ICH Guideline for Good Clinical Practice E6(R1) defines an adverse event (AE) as:

Any untoward medical occurrence in a patient or clinical investigation subject administered a pharmaceutical product and which does not necessarily have a causal relationship with this treatment. An AE can therefore be any unfavorable and unintended sign (including an abnormal laboratory finding), symptom, or disease temporally associated with the use of a medicinal product, whether or not considered related to the medicinal product.

As this is a study that does not include a pharmaceutical product intervention, this definition would include AEs that occur as a result of protocol procedures and protocol treatment.

A serious adverse event (SAE) is any AE that:

- Results in death
- Is immediately life-threatening

This term refers to an event in which the subject was at risk of death at the time of the event; it does not refer to an event that may have led to death.

- Requires inpatient hospitalization or prolongation of existing hospitalization

In general, hospitalization signifies that the subject has been detained (usually involving at least an overnight stay) at the hospital or emergency ward for observation and/or treatment that would not have been appropriate in an outpatient setting.

- Results in persistent or significant disability/incapacity
The term disability means a substantial disruption of a person's ability to conduct normal life functions.

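### Alpha passes only from mean 1/RT to ESS; passing it both ways would never reject less, keeps familywise error within 0.05, and would add about 3 to 5 points of power for mean 1/RT if ESS responds as planned

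*Combined protocol and SAP*

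**What the plan says.** Section IV (Data Analysis), Sample size, names "mean reciprocal reaction time (mean 1/RT) and ESS, which are our co-primary endpoints" and sets the overall error rate: "We will control the type I error rate at 0.05 for assessing the primary endpoints conservatively using a Bonferroni correction". Each endpoint is powered on its own half share. For reaction time the plan claims "80% power to detect a change of 0.90 standard deviations in mean 1/RT with an alpha level of 0.025"; for ESS, with an assumed SD of 3.2, it claims the same power "to detect a change in ESS of 2.87 with an alpha level of 0.025 using a two sided t-test".

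Statistical Methods puts mean 1/RT first and ESS second, citing a fixed-sequence Bonferroni procedure. An endpoint that has not crossed early is tested at 0.023 at the final analysis. The only exception favours ESS: "If there is a significant difference in mean 1/RT, then ESS will instead be tested at the total remaining alpha level, 0.046".

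Interim Analysis (34 completers) has the same structure. Mean 1/RT must reach |Z| > 2.813 whatever ESS shows. If it does, "early efficacy for ESS will be evaluated and calculated using the total available type I error rate of 0.05", which lowers the ESS boundary to 2.48; otherwise ESS also faces 2.813. The trial stops only if both endpoints cross.

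ESS therefore keeps its own 0.023 when mean 1/RT fails, and an ESS win can be declared. No sentence passes the alpha released by that win to mean 1/RT.

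**The concern.** Vigilance is the first objective (section I) and the stated hypothesis (section II), yet mean 1/RT is the endpoint that never receives recycled alpha. At equal planned effects the rule gives ESS the higher power of the two. Because early stopping needs both endpoints, an interim with ESS beyond 2.813 and mean 1/RT between 2.48 and 2.813 does not stop, while the mirror-image result does. With about 50 evaluable patients, a few points of power that need no extra patients are worth having, and the plan gives no reason for passing alpha one way only.

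**Working it through.** **Inputs.** From section IV: "We will enroll a total of 60 patients with 30 randomized to each group"; "We assume a loss to follow up rate of 15" per cent, so 60 × 0.85 = 51, taken by the plan as at least 50 (25 per arm); effects 0.90 SD for mean 1/RT and 2.87/3.2 = 0.897 SD for ESS; interim at 34/50 = 0.68 of the information; interim cuts 2.813 and 2.48; final two-sided levels 0.023 and 0.046. The correlation between the endpoints is not given, so 0 to 0.9 is assumed and shown.

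**1. The plan's power.** Two-sided t-test, 48 df, noncentrality d × √(25/2). For mean 1/RT this is 0.90 × 3.536 = 3.182 against a critical value of 2.314 at 0.025: power 0.804. For ESS it is 0.897 × 3.536 = 3.171: power 0.801. The stated 80% reproduces for both.

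**2. The plan's boundaries.** O'Brien-Fleming-type spending, 4[1 − Φ(z(1−α/4)/√0.68)], gives 0.0049 for α = 0.025 (|Z| = 2.813, final level 0.0235) and 0.0131 for α = 0.05 (|Z| = 2.480, final level 0.0460). These match the plan, to rounding for 0.023.

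**3. Why the rule is dominated.** View both rules as closed tests. The joint null is rejected under either rule if at least one endpoint crosses its 0.025-share boundary (2.813, then 0.023). After that, ESS is judged on the full-0.05 boundary (2.48, then 0.046) under both rules. Mean 1/RT is judged on the 0.025 boundary under the plan and on the 0.05 boundary under two-way passing. The second is easier to cross at each look and still has level 0.05, so two-way passing loses no rejection and keeps familywise control.

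**4. Hand check, final analysis only, correlation 0.** The gain is the chance that mean 1/RT falls between the two levels, times the chance that ESS wins at 0.023. The t-test power for mean 1/RT is 0.869 at 0.046 and 0.795 at 0.023; for ESS at 0.023 it is 0.792. Gain = (0.869 − 0.795) × 0.792 = 0.059, or 5.9 points. Simulated t-tests at these levels give +5.9, +5.3, +4.8, +4.3 and +3.4 points at correlations 0, 0.3, 0.5, 0.7 and 0.9.

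**5. Both looks, the plan's own cuts.** Bivariate normal simulation, 17 then 25 per arm, about 0.9 SD on mean 1/RT:

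| True ESS effect | Correlation | Mean 1/RT power, as written to two-way | Gain (points) |
|---|---|---|---|
| 0.9 SD | 0 | 81.9% to 87.1% | +5.2 |
| 0.9 SD | 0.3 | 81.9% to 86.6% | +4.7 |
| 0.9 SD | 0.7 | | +3.8 |
| 0.9 SD | 0.9 | | +3.0 |
| 0.6 SD | 0.3 | | +2.0 |
| 0.3 SD | 0.3 | | +0.4 |
| none | 0.3 | | +0.2 |

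The absolute levels run slightly high because the simulation is on the normal scale; the gains are what matter. ESS power is identical under both rules, and so is the chance of at least one win. If mean 1/RT itself falls short of plan at 0.6 SD, its gain is about 5 points when ESS is also at 0.6 SD, and its power rises from about 44% to 54% when ESS is at 0.9 SD.

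**6. Error and early stopping.** With both nulls true, familywise error is about 0.049 under either rule. With ESS effective at 0.9 SD and mean 1/RT null, the false-positive rate for mean 1/RT rises from about 0.025 to about 0.044 (correlation 0.3); if ESS always wins it reaches 0.050. The plan already accepts that 0.050 for ESS in the mirror case. At the planned effects, early stops rise from 23 / 28 / 33% to 29 / 34 / 39% at correlations 0 / 0.3 / 0.6.

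**The case against.** The strongest reply is that nothing here is wrong. The plan names a recognised procedure, cites it, fixes the order and controls familywise error at 0.05. Its 80% power is claimed at 0.025 per endpoint and never counted on recycled alpha. All of that stands: this is a forgone gain, not a defect. A reader might infer that the trial is invalid or that mean 1/RT falls below its stated design power; the documents support neither.

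A reader might also infer that a win on ESS is wasted. It is not. ESS is tested at its own level even when mean 1/RT fails, and a significant ESS result stands. Only the alpha it releases goes unused.

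Nor is the change free in every respect. A sponsor may prefer to hold the error rate for the hypothesis endpoint near 0.025 even when ESS works, and stopping more often at 34 patients leaves less data on secondary outcomes and side effects. Those are legitimate reasons to keep the one-way rule, but the plan states neither. Its ordering of the endpoints is not itself a reason, because mean 1/RT can stay first under two-way passing.

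**Conclusion.** The point holds as a cheap improvement in efficiency. Dominance in rejections follows from the equal shares and the plan's own boundaries and needs no assumption about effects. The size does: about 3 to 5 points for mean 1/RT assumes both endpoints near their planned effects, with the higher figure at low correlation. Five points should not be quoted without that condition, since the gain falls to about 2 points at an ESS effect of 0.6 SD (correlation 0.3) and nearly vanishes if ESS does not respond. The cost in error is confined to mean 1/RT when only ESS works, and stays within 0.05.

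**What to change.** In section IV, Statistical Methods, replace the one-way sentence with:

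*If either endpoint is declared significant, at the interim or at the final analysis, the other is tested at the final analysis at 0.046 instead of 0.023.*

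The trigger should be a declared win at either look, not significance at 0.023, so that it covers an endpoint that crossed only at the interim while the trial continued.

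In Interim Analysis, replace the conditional ESS boundary with:

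*If either endpoint crosses |Z| > 2.813, the other is tested against |Z| > 2.48; the trial stops if both cross.*

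Update the description and citation of the sequential procedure to Holm or graphical recycling with group-sequential boundaries. Mean 1/RT may still be listed first.

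The cost is a few sentences and no patients or data. The change must be made before any unblinded look. The document is dated August 2021 and does not say whether the interim has taken place; if it has, the rule should stay as written. A sponsor who prefers the tighter error rate on mean 1/RT can keep the one-way rule and state that reason.
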